We are studying whether water-soluble cinnamon extract (Cinnulin PF) plus standard of care aggressive lifestyle therapy is effective in lowering blood glucose when compared to placebo plus standard of care aggressive life style therapy. Eligible subjects will be recruited from any form and any stage of “standard” lifestyle intervention for pre-diabetes at an individual base. “Standard” lifestyle intervention for pre-diabetes could include Group Lifestyle Balance (GLB), nutrition classes, Better Body/Better Life, or anything an investigator certifies as standard practice at that base. Subjects will take either 1 gram (2-500 milligram (mg) capsules) of water-soluble cinnamon extract (Cinnulin PF) or 2 placebo pills (gelatin capsule filled with wheat bran) once a day for 1 year plus 1 additional year of follow-up. This is a randomized, double-blind, multicenter, placebo-controlled study which will enroll subjects at the Mike O’Callaghan Military Medical Center at Nellis AFB (Nellis AFB). All subjects will be Nellis AFB DoD beneficiaries. Informed Consent and HIPAA Authorization will be obtained. After randomization, subjects will receive either 1 gram (2-500 mg capsules) of water-soluble cinnamon extract or placebo from the pharmacy--thus investigators and subjects will be blinded as to if they are taking Cinnulin PF or 2 placebo pills. Subjects will be permitted to have usual medical care for other co-morbid, preventive, and acute conditions. Analysis will be performed using intention-to-treat principles for missing data (the carry-forward method to impute missing data will be used). Subjects will bring in any remaining water-soluble cinnamon extract or placebo to determine adherence rates to the study protocol.

5. Subjects:

Subjects will be recruited from any form and any stage of “standard” lifestyle intervention for pre-diabetes at an individual base. “Standard” lifestyle intervention for pre-diabetes could include Group Lifestyle Balance (GLB), nutrition classes, Better Body/Better Life, or anything an investigator certifies as standard practice at that base. No special populations (i.e. children, prisoners, pregnant women, mentally disabled persons, or economically or educationally disadvantaged persons) will be eligible for this study.

6. Inclusion/exclusion criteria:

Inclusion:

- Patients will be Nellis AFBDOD beneficiaries, ages 18-65 years.

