2.1. Associate Investigators (AI): See attached A2 Study Personnel Form

2.2. Research Assistants (RA) & Coordinators (RC): See attached A2 Study Personnel Form

2.3. The research relevance of this protocol focuses on:

Diagnosis Treatment Medical Utilization/Managed Care Prevention Medical Readiness Other

2.4. Location(s):

a. Collaborating Facilities: None.

b. Air Force Sites seeking Regional IRB:

Air Force Sites	Name	Email	Phone
Nellis Air Force Base	[name], MBA/HCM, CCRP, CCRC	[contact]	[contact]

c. List study sponsors: Integrity Nutraceuticals, Inc. and AFMSA/SG9S

3. Research Plan:

3.1. Purpose:

The purpose of this study is to assess whether water-soluble cinnamon extract plus aggressive lifestyle intervention is effective in lowering blood glucose in pre-diabetic patients when compared to aggressive lifestyle therapy plus placebo.

3.2. Hypotheses, Research Questions or Objectives:

Does water-soluble cinnamon extract have an effect on fasting glucose, Hemoglobin A1c, lipid panel, and waist circumference in pre-diabetic patients who are already undergoing aggressive lifestyle therapy?

This study has the following goals:

1. Determine the length of time to diagnosis of diabetes using any of the ADA criteria.
2. Determine:
 - a) Fasting glucose
 - b) Hemoglobin A1C
 - c) LDL cholesterol, and
 - d) Waist circumference (in inches)

3.3. Significance:

Lowering hemoglobin A1c is correlated with reduced complications in Type 2 diabetes (e.g., retinopathy, nephropathy, neuropathy, vascular disease, and death). Water-soluble cinnamon extract is inexpensive, readily available, generally recognized as safe, and a non-pharmacological approach to management. According to the 2010 American Diabetes Association Guidelines, lifestyle intervention is the most effective way for diabetes. Historically, it has been difficult for subjects to adhere to lifestyle education programs and sustain meaningful weight loss without using significant resources, as in the Diabetes Prevention Study (NEJM, 2002).

3.4. Military Relevance:

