BLOOD TEST OUTSIDE OF NORMAL REFERENCE RANGE: Research Coordinators at each site will print the blood test results and place in the subject's folder. If any of these results are outside of the normal reference range noted by their lab, they will place a telephone consult for the subject's Primary Care Manager (PCM).

DISPOSAL OF STUDY RELATED PILLS: Subjects will return any remaining study-related pills directly to the Research Coordinator or Principal Investigator. The Research Coordinator or Principal Investigator will be responsible for disposing of the study-related pills. The preferred method of disposal is to have the Pharmacy dispose of them. If the Pharmacy is unable to dispose of them, they will provide directions on safe disposal for the Research Coordinator or Principal Investigator to follow.

OTHER ITEMS: If at any time, a site needs more study medication, they should contact the main site at the Nellis AFB and request. Integrity Nutraceuticals should not be contacted directly. Prior to ordering any standard of care labs, study staff will verify in AHLTA that the subject did not have that lab test within the previous timeframes documented in the study visits above. In addition, CHCS has alerts built in that will alert the person entering the lab test that there is a pending order.

Subjects will take their water-soluble cinnamon extract or placebo daily and will be permitted to have the usual medical care for other co-morbid and acute conditions if applicable. Analysis described above using intention-to-treat principles for any missing data will be used (we will use the carry-forward method to impute missing data).

The placebo will be a gelatin capsule filled with wheat bran, which does not increase the risks to subjects.

Each site's Laboratory will be responsible for analyzing blood samples obtained at their site for this study. Samples will be labeled as they would for standard laboratory draws. All Laboratories follow Clinical Laboratory Improvement Amendments (CLIA) procedures when processing laboratory specimens mentioned in this research project.

This study involves the use of an investigational product (IP) called Cinnulin PF (water-soluble cinnamon extract). This means that the product has not been approved by the Food & Drug Administration (FDA) for preventing or delaying the onset of

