6.2. Sample size estimation/power analysis:

A priori power for H₀₁ was assessed using G*Power Version 3.0.10¹. The results indicate 214 subjects per group with 8 repeated measures for a total sample size of 3424 will achieve a power of approximately 0.99 to detect a small effect size of 0.10 at α = 0.0004.

A priori power for H₀₂ was assessed using the method described by Glantz² to calculate sample size for a two-sample log-rank test to detect differences in the time to event. Based on this design, it will require a minimum of 214 subjects per group to detect a difference between a 17.5% conversion in the Placebo + lifestyle and an 11.5% conversion in the Cinnulin + lifestyle group at α = 0.05 (one-sided) and power of 0.80.

We are enrolling 557 subjects total, for an expected 428 completing the study. We estimate 129 subjects' will either withdraw consent or drop out of the study.

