6.3. Statistical Analysis: Statistical Analysis Plan

Protocol	Assessment of the effect of lifestyle intervention plus water-soluble cinnamon extract on lowering blood glucose in pre-diabetics: A randomized, double-blind, multicenter, placebo controlled TRIAL.
Principal Investigator(s)	Lt Col [name], USAF, MC 99 th MDG
Statistical Analysis Plan	[name], Ctr AFMSA/SG5M South
Statistical Analysis	[name], Ctr AFMSA/SG5M South

Technical Objective: The objective of this study is to compare Cinnulin PF, a cinnamon extract, in combination with a lifestyle management program, to a placebo and life style management program, and to evaluate the prevention or delay the development of Type 2 diabetes in persons with pre-diabetes.

Sample: Subjects will be a random sample of males and females between the ages of 18-65 years with a diagnosis of pre-diabetes seen in certain Air Force medical treatment facilities. The subjects are presumed to be randomly selected from the population of patients obtaining similar care at all Air Force medical treatment facilities.

Hypothesis:

H₀₁ – No difference in means of continuous dependent variables between and among treatment groups
H₀₂ – Cinnulin + Life Style and Placebo + Life Style groups have identical survival functions for the time to reach the Type 2 diabetes conversion event.

Study Design: The experimental design of this study is a mixed effects, randomized complete block design with repeated measures. Subject is a random effect as the subjects are a sample randomly selected and randomly assigned to a treatment group. Fixed effects are treatment group and time of repeated measure as these effects cannot be generalized to other treatments and times. Subjects will be randomly assigned to each treatment group.

Factors:

1. Subject
2. Treatment: Cinnulin PF + Life Style Management versus Placebo + Lifestyle Management
3. Repeated Measurements: Laboratory and physical measurements obtained from each subject at fixed intervals for the duration of the study (N=8).

¹ Faul F, Erdfelder E, Lang A-G, Buchner A. G*Power 3: A flexible statistical power analysis program for the social, behavioral, and biomedical sciences. *Behavior Research Methods*. 2007; 39 (2): 175-191.

² Glantz SA. *Primer of Biostatistics*. McGraw-Hill, 2002, 438-440.

Outcome Variables:

1. Diabetic indicators
 - a. Glucose
 - b. Hemoglobin A1c
 - c. Lipid panel (cholesterol, triglycerides, HDL, LDL)
 - d. Waist circumference

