2. Type 2 diabetes conversion: Yes/No

Other Variables of Interest among Subjects

1. Subject Demographics
 - a. Age (years)
 - b. Marital Status (single versus married)
 - c. Gender
 - d. Race/Ethnicity (African American, European American, or Hispanic, 2 parameters)
 - e. Specialty codes (categorized into office work, logistics, or combat specialties, 2 parameters)
 - f. Military Grade (Officer grades categorized into company, field or higher ranks; enlisted into E1 – E6 or E7 – E9).

Sample Size Estimation and Power Analysis: A priori power for H_01 was assessed using G*Power Version 3.0.10³. The results shown below indicate 214 subjects per group with 8 repeated measures for a total sample size of 3424 will achieve a power of approximately 0.99 to detect a small effect size of 0.10 at $\alpha = 0.0004$.

Input:	Effect size f	=	0.1
	β/α ratio	=	4
	Total sample size	=	3424
	Number of groups	=	2
	Repetitions	=	8
	Corr among rep measures	=	0.8
Output:	Noncentrality parameter λ	=	41.503030
	Critical F	=	12.389225
	Numerator df	=	1.000000
	Denominator df	=	3422
	α err prob	=	0.000437447
	β err prob	=	0.00174979
	Power (1- β err prob)	=	0.998250

[figure not shown]

Figure 1. rANOVA Power, $\beta = 0.002$, $\alpha = 0.0004$, 214 subjects per group

Post hoc analyses to evaluate differences within clinically significant time intervals will be tested with one-tailed t-tests for independent samples. The power analysis, using G*Power Version 3.0.10⁴, is shown below and shows 214 subjects per group will achieve a power of approximately 0.85 to detect a small effect size of 0.20. To lessen the probability of a false negative, a β/α ratio of 1 was employed.

t tests - Means: Difference between two independent means (two groups)

Analysis:	Compromise: Compute implied α & power		
Input:	Tail(s)	=	One
	Effect size d	=	0.2
	β/α ratio	=	1
	Sample size group 1	=	214
	Sample size group 2	=	214
Output:	Noncentrality parameter δ	=	2.068816
	Critical t	=	1.035015
	Df	=	426
	α err prob	=	0.150624
	β err prob	=	0.150624
	Power (1- β err prob)	=	0.849376

³ Faul F, Erdfelder E, Lang A-G, Buchner A. G*Power 3: A flexible statistical power analysis program for the social, behavioral, and biomedical sciences. *Behavior Research Methods*. 2007; 39 (2): 175-191.

⁴ Ibid.

[figure not shown]

Figure 2. *t*-test Power, $\beta = 0.15$, $\alpha = 0.15$, 214 subjects per group

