A priori power for H_02 was assessed using the method described by Glantz⁵ to calculate sample size for a two-sample log-rank test to detect differences in the time to event. Based on this design, it will require a minimum of 214 subjects per group to detect a difference between a 17.5% conversion in the placebo + lifestyle and an 11.5% conversion in the cinnulin + lifestyle group at $\alpha = 0.05$ (one-sided) and power of 0.80.

Power Analysis Log-Rank Test for Two Samples	
α	0.050
$Z_{.05(2)}$	1.64
$1-\beta$	0.80
$Z_{.80(\text{upper})}$	-0.842
$S_2(\infty)$	0.885
$\text{Ln}S_2(\infty)$	-0.122168
$S_1(\infty)$	0.825
$\text{Ln}S_1(\infty)$	-0.192372
ψ	0.6350597
d (primary endpoint events) =	124
n (sample size to achieve this number of events) =	428
Groups/Treatments	2
Subjects required per group/treatment	214

Steps of Analysis

Descriptive statistics: Sample means and standard errors of measurement of interval variables will be calculated, and frequency distributions of nominal variables will be calculated and graphed for the total sample and for the Cinnulin/Lifestyle Management groups. Homogeneity of the groups will be tested with a two-tailed *t*-test and two-tailed Fisher's exact test for interval and nominal variables respectively.

Hypothesis Testing

H_01 – This hypothesis will be tested by a mixed effects repeated measures analysis of variance (rANOVA).

H_02 – This hypothesis will be tested by developing Kaplan-Meier survival curves and survival functions compared with a log-rank test.

Post Hoc Tests: In the event H_01 is rejected, contrasts will be used to investigate effects and differences within clinically significant time intervals. In the event multiple univariate tests are used to investigate effects, the Bonferroni⁶ or Holm's method⁷ will be used to correct the level of significance for multiple comparisons.

Analysis Tools:

SAS Version 9.2 for Windows (SAS Institute, Cary, North Carolina)

R Version 2.13.1 (R Foundation for Statistical Computing)

Microsoft Excel (Microsoft Corporation, Seattle, Washington)

6.4 Number of Subjects:

Number of subjects recruited at WHASC	46
---------------------------------------	----

⁵ Glantz SA. *Primer of Biostatistics*. McGraw-Hill, 2002, 438-440.

⁶ Abdi H. Bonferroni and Šidák. Corrections for multiple comparisons. In N.J. Salkind (ed.). *Encyclopedia of Measurement and Statistics*. 2007; Thousand Oaks, CA: Sage.

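### The SAP gives no censoring rule for time to diabetes (H02), and the plan's only missing-data rule, carry-forward, would if applied as written keep event-free drop-outs at risk to Month 24

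*Combined protocol and SAP*

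**What the plan says.** Protocol section 3.2 makes time to diabetes the first goal: "Determine the length of time to diagnosis of diabetes using any of the ADA criteria". In the SAP (section 6.3), H02 states that the two arms have "identical survival functions for the time to reach the Type 2 diabetes conversion event". The test step reads: "This hypothesis will be tested by developing Kaplan-Meier survival curves and survival functions compared with a log-rank test". The SAP's list of outcome variables enters the same outcome as "Type 2 diabetes conversion: Yes/No".

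The missing-data rule stands outside the SAP, in two places. The brief summary (Protocol Summary, item 4) says that "the carry-forward method to impute missing data will be used". Section 3.6, under Other Items, describes analysis "using intention-to-treat principles for any missing data will be used (we will use the carry-forward method to impute missing data". Neither sentence is limited to H01 or to continuous variables.

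On losses, section 6.2 says: "We estimate 129 subjects' will either withdraw consent or drop out of the study". That is out of 557 enrolled, with 428 expected to complete.

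No section gives a censoring rule, a definition of the event date, or a rule for subjects lost before the last visit at Month 24. Three further provisions matter. Diabetes is defined by thresholds on fasting glucose, HbA1c or OGTT (section 3.6.7). Subjects who convert are taken out of the study, and subjects who only stop their capsules stay in follow-up (both section 3.6).

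**The concern.** Kaplan-Meier and the log-rank test are valid because a subject counts as at risk only while an event could still be observed. Someone who leaves at Month 6 without diabetes should leave the risk set after the last assessment. Carry-forward does the opposite: the last value fills every later visit.

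Nobody has to decide to carry conversion status forward for this to happen. Glucose and HbA1c plainly fall under the rule, and conversion is read off them. If a drop-out's pre-diabetic values are filled in to Month 24 and conversion is derived from the completed data set, the result is no conversion at every later visit, and the follow-up time passed to the survival procedure is 24 months. Converters already have their event and capsule-stoppers are still tested, so the rule acts on H02 mainly through the event-free withdrawals and drop-outs, the very subjects who should be censored.

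Two things are at stake. The reported conversion percentages would be too low in both arms. And if one arm loses more subjects than the other, that arm would look better, because its lost subjects stay in the denominator and can no longer convert.

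**Working it through.** **Inputs.** From section 6.2 and the SAP: conversion 17.5% (placebo) and 11.5% (Cinnulin); one-sided alpha 0.05; 557 enrolled, 129 lost. From section 3.6: visits every 90 days, the last at Month 24, and blocked allocation to roughly equal arms. Assumed, because the documents do not say: the two rates are 24-month risks, hazards are constant, and drop-out is independent of conversion. The only annual rate given, 7% in section 3.5, yields 1 − 0.93² = 13.5% over two years and 1 − 0.93³ = 19.6% over three, so it does not settle the horizon of the 17.5%.

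**The plan's own figures.** 129/557 = 23.2%, and 557 − 129 = 428, as stated. The hazard ratio is ln 0.885 / ln 0.825 = 0.122168/0.192372 = 0.635, as stated. Events: (1.64 + 0.842)² × (1.635/0.365)² ≈ 124, as stated. The total of 428 does not reproduce: 124/(2 − 0.825 − 0.885) = 427.6 is a number per group. That is a separate matter, but it explains why the simulated power below is near 0.59 and not 0.80.

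**Conversion under carry-forward, equal drop-out.** Let H = −ln(1 − p) be the cumulative conversion hazard to Month 24 and G = −ln(1 − 129/557) = 0.2634 the cumulative drop-out hazard. The share seen to convert before leaving, with everyone else counted as diabetes-free, is

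H/(H + G) × [1 − exp(−(H + G))].

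- Placebo: 0.1924/0.4558 × (1 − 0.825 × 0.7684) = 0.4220 × 0.3661 = 15.4% to 15.5%.
- Cinnulin: 0.1222/0.3856 × (1 − 0.885 × 0.7684) = 0.3168 × 0.3200 = 10.1%.

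With detection only at the quarterly visits, a subject who converts and leaves between two visits is also missed. Simulation (557 subjects, 4,000 runs) then gives 15.2% and 10.0%. Censoring at the last visit recovers 17.5% and 11.5%. The difference shrinks from 6.0 to 5.2 points. If every drop-out left straight after baseline, the limits would be 17.5% × 0.768 = 13.4% and 11.5% × 0.768 = 8.8%.

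**Log-rank test.** Same simulation; one-sided rejection rate in favour of Cinnulin:

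| True conversion, placebo / Cinnulin | Drop-out, placebo / Cinnulin | Censored | Carried forward |
|---|---|---|---|
| 17.5% / 17.5% | 23.2% / 23.2% | 0.051 | 0.051 |
| 17.5% / 17.5% | 18% / 28.3% | 0.049 | 0.096 |
| 17.5% / 17.5% | 15% / 31.3% | 0.052 | 0.138 |
| 17.5% / 17.5% | 31.3% / 15% | 0.052 | 0.016 |
| 17.5% / 11.5% | 23.2% / 23.2% | 0.592 | 0.583 |
| 17.5% / 11.5% | 31.3% / 15% | 0.598 | 0.404 |

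Smaller gaps with no true effect, carried forward: 0.056 at 22.2% versus 24.2%; 0.063 and 0.070 in two separate runs at 21% versus 25.4%. The Monte Carlo standard error near 0.05 is √(0.05 × 0.95/4000) = 0.003. Independent repeats of the larger scenarios agreed within simulation error (0.097 at 18% versus 28%; 0.136 and 0.137 at 15% versus 31%).

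**The case against.** A reader might infer that the plan makes H02 a plain Yes/No status and counts drop-outs as diabetes-free to Month 24. The documents do not support that. The first goal, the wording of H02, the sample-size method and the named test all make it a time-to-event outcome. A Yes/No line in a variable list is simply the event indicator that Kaplan-Meier needs. No sentence says that conversion status is carried forward, the SAP does not repeat the carry-forward rule, and that rule sits most naturally with the repeated measurements of H01. A statistician running Kaplan-Meier would ordinarily censor at last contact. All of this stands, and it makes the defect conditional. It does not remove it: survival software censors at whatever last time the data set holds, and after carry-forward that time is Month 24.

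A reader might also infer that the log-rank test is biased as planned. That needs unequal drop-out, and the documents give only the total. The trial is double-blind and keeps subjects who stop capsules in follow-up, which closes one obvious route to imbalance. With about 278.5 per arm, the standard error of the difference in drop-out is √(2 × 0.232 × 0.768/278.5) = 3.6 points. A 16-point gap is therefore about 4.5 standard errors from equality and a 10-point gap about 2.8; these are sensitivity cases, not forecasts. A 4.4-point gap is only about 1.2 standard errors, so a systematic difference of that size could hardly be told from chance. Its cost is small: an error of 0.06 to 0.07 in place of 0.05.

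**Conclusion.** The point holds as a conflict between two parts of the plan. The analysis named for H02 requires censoring, the only stated missing-data rule works against it, and nothing says which governs for 23.2% of the subjects. Left open, the choice could be made after the data are seen.

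If carry-forward were applied to H02, the certain effect is on the estimates: about 15.2% and 10.0% in place of 17.5% and 11.5%, a relative fall of about 13% in each arm (15.2/17.5 = 0.87; 10.0/11.5 = 0.87). With equal drop-out, power and type I error hardly move. Bias in the test is a further and conditional step. It grows from slight at a gap of a few points to a one-sided error of about 0.14 at 15% versus 31%, and with the imbalance reversed it costs power.

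All sizes rest on 24-month risks, constant hazards, drop-out independent of conversion, and assumed splits of drop-out by arm. The documents do not establish that drop-outs will be counted as diabetes-free, nor that drop-out will be unequal. They leave the first possible and say nothing on the second.

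**What to change.** Add to the H02 step in SAP section 6.3: time runs from randomisation to the first result that meets the protocol's diabetes definition; a subject without an event is censored at the last assessment made before withdrawal (study-visit glucose or HbA1c, or any other available test in the definition); carry-forward does not apply to H02. Limit the carry-forward sentences in the brief summary and in section 3.6 (Other Items) to match.

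Use the date of the test, not the visit number. Section 3.6 accepts results up to two weeks old, and subjects who resume after a long break rejoin at an earlier point in the visit sequence. The two worked examples of resumption, under adherence and under pregnancy, name different next visits and must be reconciled.

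The cost is a few sentences, with no new visits or tests. The visit lists do not name test dates as recorded items, so confirm that the dates are in the data set or can be taken from the laboratory reports. Intervals will be slightly wider late in follow-up. The change should be made before treatment codes are released for analysis.

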3.6.4. Date(s): April 2012-April 2018

3.6.5. Source of Research Material:

Source of Research Material per Participant (Procedures)	# Routine Care	# Research Driven	# Total Procedures
Group 1 Only: 1 gram (2-500 mg capsules) water-soluble cinnamon extract (Cinnulin PF) (once a day for 1 year)	0	1 year	1 year
Group 2 Only: 2 placebo pills (once a day for 1 year)	0	1 year	1 year
Fasting glucose	0	3	3
Fasting comprehensive metabolic panel	3	3	6
Hemoglobin A1C	4	5	9
ECG	0	2	2
Lipid panel	4	5	9
Study Medication Diary	0	4	4
RAND 36-Item Health Questionnaire	0	3	3

"All specimens collected at Nellis AFB will be kept at Nellis AFB and handled and disposed of in accordance with federal regulations."

3.6.6. Subjects:

We will recruit male and female subjects Nellis AFB between the ages of 18-65 years with a diagnosis of pre-diabetes. Eligible subjects will be recruited from any form and any stage of "standard" lifestyle intervention for pre-diabetes at an individual base. "Standard" lifestyle intervention for pre-diabetes could include Group Lifestyle Balance (GLB), nutrition classes, Better Body/Better Life, or anything an investigator certifies as standard practice at that base. No special populations (i.e. children, prisoners, pregnant women, mentally disabled persons, or economically or educationally disadvantaged persons) will be eligible for this study. There are currently 2,950 diabetic patients empaneled for care at Nellis AFB. Several thousand more are pre-diabetic--many of these will likely attain the diagnosis of diabetes within 36 months.

3.6.7. Inclusion/Exclusion Criteria:

Inclusion:

- Patients will be Nellis AFB DoD beneficiaries between the ages of 18-65 years.
- Diagnosis of pre-diabetes (defined as a fasting plasma glucose (FPG) 100-125mg/dl or hemoglobin A1C 5.7-6.4% or a 2-hour oral glucose tolerance test (OGTT) 140-199).

Exclusion:

- Patients who are less than 18 yrs of age or greater than 65 years of age
- Patients who are known to have or develop during the study any of the following upon review of their medical record:
 - o Diabetes Mellitus (defined as fasting plasma glucose (FPG) ≥126mg/dl, hemoglobin A1C ≥6.5%, or a 2-hour oral glucose tolerance test (OGTT) ≥200mg/dl)

- o Stage 3 kidney disease or worse
- o Renal insufficiency defined as a glomerular filtration rate (gfr) of less than 60ml
- o Celiac disease
- o Insulinoma
- o Cushing's disease
- o Hyperthyroidism
- o Acromegaly
- o Pheochromocytoma
- o Addison's disease

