⁷ Holm, S. 1979. A simple sequential rejective multiple test procedure. *Scand. J. Statistics*, 6: 65-70.

Number of subjects recruited at Nellis AFB	106
Number of subjects recruited at DGMC	76
Number of subjects recruited atEglin (actual)	53
Numerb of subject recruited at Offutt	2

TOTAL NUMBER OF SUBJECTS: 557 (nation-wide/study-wide): **428** (completing the study)

7. Duration of Study: Approximate duration of the study: 6 years

8. Intramural Funding/Local Support Services Required:

We received a grant for Intramural funding from the AFMSA/SG9S in the amount of approximately \$639,036.36. We received a second grant from the 59MDW/ST for approximately \$618,000 over 2 years. This is to support the salaries of four Medical Assistants, costs associated with Group Lifestyle Balance training, and site monitoring visits.

9. Extramural Funding/External Support Services Required:

Integrity Nutraceuticals, Inc. will provide Cinnulin PF and placebo to Geneva Research Foundation who will administer the grant. Collaborating Institution Support: This study will be sponsored by Integrity Nutraceuticals, Inc. The collaborative research will be executed in accordance with 15 USC 3710a through a Cooperative Research and Development Agreement, (pending approval) between the 99th MDG and Integrity Nutraceuticals, Inc. Integrity Nutraceuticals, Inc. shall provide the Air Force activity: 1 gram (2-500 mg capsules) Cinnulin PF tablets for approximately 279 subjects taking once a day for 1 year (\$280,370.00) and Placebo pills for approximately 279 subjects taking once a day for 1 year (\$1,870.00) to include shipping costs to the Air Force Activity. The estimated fair market value of the support is \$282,240.00.

10. Financial Conflict of Interest: No financial conflicts of interest exist.

11. Use of an Investigational New Drug, use of a Drug for a non-FDA approved purpose, use of an investigative device or use of a placebo:

This research uses an Investigational New Drug YES NO
This research uses a FDA approved drug for a non-FDA approved purpose YES
 NO
This research uses an Investigational Device YES NO
This research uses a placebo. YES
 NO

12. Medical Research Area for the Study: (Pick as many as appropriate)

 Analytical Chemistry	 Anatomy	 Anesthesiology	 Biochemistry

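### The site recruitment listed in section 6.4 adds to 283, against a stated total of 557 with 428 completing, so the listed recruitment does not support power figures based on 214 per group

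*Combined protocol and SAP*

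**What the plan says.** Section 6.4 gives one row per site: "Number of subjects recruited at WHASC 46", "Number of subjects recruited at Nellis AFB 106", "Number of subjects recruited at DGMC 76", then 53 at Eglin, the only row marked as actual, and 2 at Offutt. No row carries a date. The closing line reads "TOTAL NUMBER OF SUBJECTS: 557 (nation-wide/study-wide" and adds 428 as the number completing.

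The same total stands in item 7 of the protocol summary and in section 6.2: "We are enrolling 557 subjects total, for an expected 428 completing the study", with 129 expected to withdraw or drop out. Sections 6.2 and 6.3 base every power statement on 214 subjects per group: about 0.99 for the repeated-measures analysis (H01), about 0.85 for the post hoc t-tests and 0.80 for the log-rank test (H02).

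Section 3.6.4 gives the study dates as "April 2012-April 2018". The document is dated 24 January 2018, and the last scheduled visit in section 3.6 is at Month 24.

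**The concern.** A total printed directly under a list of site counts should either be the sum of that list or be labelled as a different quantity. Here it is neither. The rows could be targets, achieved recruitment or a mixture, and the reader cannot tell how many subjects the trial has or expects.

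The number matters because all the stated powers depend on it. If recruitment is close to the listed figure, a null result on diabetes conversion or on the continuous outcomes excludes much less than 0.80 or 0.85 power suggests. Someone who takes 557 and 428 from the document would have no warning of this.

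**Working it through.** **1. The sum.** 46 + 106 + 76 + 53 + 2 = 283.
- Against the stated total: 557 − 283 = 274 missing; 283/557 = 0.508.
- Against the completers: 428 − 283 = 145 short before any loss.
- The planning total is consistent in itself: 428 + 129 = 557.
- Planned loss is 129/557 = 23.2%. Applied to the listed recruitment, 283 × 428/557 ≈ 217 would complete.
- No other site is given a count. The brief summary and sections 2.4 and 3.6.3 name only Nellis AFB as the present site.

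**2. The calendar.** An April 2018 end less 24 months means that a subject starting after about April 2016 cannot reach the last visit within the stated dates. Enrolment after the document date of January 2018 therefore adds no 24-month completers.

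**3. Log-rank test (H02), one-sided 0.05.** Inputs are from the table in section 6.3.
- ψ = ln(0.885)/ln(0.825) = 0.122168/0.192372 = 0.635, as stated.
- Events: d = (1.64 + 0.842)² × [(1 + ψ)/(1 − ψ)]² = 123.7, or 124 as stated.
- Subjects: 124/(2 − 0.825 − 0.885) = 124/0.29 = 427.6, or 428 as stated. The plan's arithmetic thus counts 0.29 events per subject.
- Power = Φ(√d × (1 − ψ)/(1 + ψ) − 1.645), where (1 − ψ)/(1 + ψ) = 0.2232.

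With equal groups, the average of 17.5% and 11.5% is 0.145 events per subject, half of the plan's 0.29. Both counts are shown so that the effect of recruitment can be read separately from that difference.

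| Subjects | Events at 0.29 | Power | Events at 0.145 | Power |
|---|---|---|---|---|
| 428 | 124.1 | 0.80 | 62.1 | 0.55 |
| 283 | 82.1 | 0.65 | 41.0 | 0.41 |
| 217 | 62.9 | 0.55 | 31.5 | 0.35 |

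**4. Post hoc t-test, d = 0.20, one-tailed.** The noncentrality is 0.2 × √(n/2), with n per group. At 214 it is 2.069, and with implied α = 0.1506 the power is 0.849, as stated. Holding that α:
- 283 subjects (141.5 per group): noncentrality 1.682, power 0.74.
- 217 subjects (108.5 per group): noncentrality 1.473, power 0.67.

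**5. Repeated-measures analysis (H01).** The stated output follows from λ = f² × N × 8/(1 + 7 × 0.8), with f = 0.1 and N = 3424 = 428 × 8: λ = 41.503 and power 0.998 at α = 0.00044. On the same counting, 283 × 8 = 2264 gives λ = 27.44 and power 0.957, and 217 × 8 = 1736 gives λ = 21.04 and power 0.86. Entering 3424 observations as the sample size is a separate question and is not part of this point.

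The planned 428 is a number completing, so 217 is the like-for-like comparison. The 283 row is the most favourable case, in which every listed subject contributes fully.

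**The case against.** The strongest reply is that 557 and the rows are different quantities. The rows are worded as past recruitment, while 557 is planned enrolment. It agrees with 428 + 129 and with the product supply in section 9 for about 279 subjects per arm. On that view the list is an accrual table with poor labels, not a faulty addition. This may be so, but the document does not say it, and the site list then falls well short of the plan without comment.

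A reader might infer three stronger things that the documents do not support.

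- **That the trial has only 283 subjects.** Only the Eglin row is marked as actual and no cut-off date is given. The figure is listed recruitment, not a confirmed final number.
- **That the shortfall makes the power calculations wrong.** They are labelled a priori and are conditional on 214 per group. A shortfall leaves that condition unmet; it is not a calculation error.
- **That recruitment takes log-rank power from 0.80 to 0.41.** At a 14.5% mean event rate, power is already about 0.55 with the full 428. The step from 0.80 to 0.55 comes from the event count in the sample size formula, which is a separate error.

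The calendar argument also has limits. It restricts 24-month completers, not enrolment; subjects censored earlier still contribute to a log-rank test; and section 7 calls the duration approximate. It does show that enrolment after the document date could not supply the missing completers within the stated dates.

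**Conclusion.** The inconsistency stands. The listed recruitment of 283 is 51% of the stated 557 and 145 below the stated 428, and nothing in the document reconciles them. If the rows are targets, they do not add to the planned total. If they are recruitment up to the document date, 428 completers cannot come from them. Either way, the listed recruitment does not support powers based on 214 per group.

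The loss due to recruitment alone is material for the log-rank test: 0.15 to 0.25 on the plan's event count, or about 0.13 to 0.20 at the 14.5% event rate. For the t-test it is about 0.11 to 0.18. On the plan's own counting the H01 power is less affected.

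These figures assume equal groups, the plan's effect sizes and significance levels, and either no loss or the plan's 23.2% loss. They describe the listed recruitment and would change if the confirmed number differs.

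**What to change.** - Label each row of section 6.4 as target or actual, with a cut-off date.
- State the number randomised at each site and in total.
- Reconcile section 6.4 with section 6.2 and item 7 of the protocol summary.
- Restate the power, or the detectable hazard ratio and mean difference, for H01 and H02 on that number. Keep the present figures, identified as the a priori plan.

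This costs wording and recalculation only. The downside is that the stated figures will be less favourable.
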